## **Inclusion and exclusion criteria**

### ***Inclusion criteria***

1. Patients of both genders aged 6 months to 6 years old.
2. ARVI based on medical examination: oral temperature of at least 38.0°C at the time of examination + total symptom severity ≥5 points.
3. First 24 hours after ARVI onset.
4. Seasonal rise in ARVI incidence.
5. Availability of signed information sheet for parents/adopters (informed consent form) for participation in the clinical trial.

### ***Exclusion criteria***

1. Suspected pneumonia, bacterial infection (including meningitis, sepsis, otitis media, urinary tract infection, etc.) requiring a prescription of antibacterial products from the first day of the disease.
2. Suspected initial manifestations of diseases with symptoms similar to ARVI at onset (other infectious diseases, flu-like syndrome at the onset of systemic diseases of connective tissue, oncohaematological and other diseases).
3. Clinical symptoms of severe influenza/ARVI requiring hospitalization.

---

 The study participants are aged 6 months to 6 years 11 months 29 days.

 Manifestation of fever, or a rise in body temperature to febrile values (≥37.6°C for oral and tympanic temperature, ≥37.4°C for axillary temperature, ≥38.0°C for rectal temperature) is considered the onset of ARVI.

4. Medical history of primary and secondary immunodeficiency; oncologic conditions.
5. Aggravation or decompensation of chronic diseases (diabetes mellitus, cerebral palsy, cystic fibrosis, primary ciliary dyskinesia, bronchopulmonary dysplasia, malformations of the respiratory and ENT organs/ear, throat, mouth, tongue, larynx, trachea, neck and salivary and thyroid glands, etc.), which affect the patient's ability to participate in the clinical study.
6. Malabsorption syndrome, including congenital or acquired lactase or other disaccharidase deficiency, galactosemia.
7. Allergy/hypersensitivity to any component of the drug product used in the therapy.
8. Course administration of the drug products specified in the section "Prohibited Concomitant Therapy" within two weeks prior to inclusion in the study.
9. Patients whose parents/adoptive parents will not fulfill the requirements during the study or follow the order of administration of the studied drug products, from the Investigator's point of view.
10. Participation in other clinical trials for 3 months prior to enrollment in this study.
11. The patient's parent/adoptive parent is a study specialist of the centre and is directly involved in the study, or is an immediate family member of the Investigator. Spouses, parents, children, or siblings, regardless of whether they are siblings or adopted are considered immediate family members.
12. The patient's parent/adoptive parent works at the OOO "NPF "Materia Medica Holding", i.e. they are employees of the Company, temporary employees on a contract basis or appointed officials responsible for conduction of the study or their immediate family members.

### **Criteria for Withdrawal or Termination**

1. Inability or refusal of patient or parents/adoptive parents to comply the Protocol requirements.
2. Necessity in medical products prohibited within the study.
3. Development of adverse event requiring product cancellation.
4. Desire of patient or parent/adoptive patient to complete the study ahead of schedule due to inefficacy of therapy or any other reason.

---

 Criteria of severe influenza/ARVI (RF MH, 2009, 2014; Union of Pediatricians of Russia, 2014; WHO 2011; CDC 20013-2014): extreme severity of disorder (toxic shock syndrome III, critical general condition disorder, decreased activity or weakness up to complete adynamia, irritability/cry when touched, lethargy, drowsiness/longer sleep, lack of eye contact during examination, refusal to eat or drink, severe tachycardia/bradycardia, tachypnea, hypo- or hyperventilation, microcirculation disorder, peripheral cyanosis, slower capillary filling of the nailfold, continuous vomiting, signs of dehydration, decreased diuresis/anuria, convulsions, symptoms of meningism), hemorrhagic syndrome (nosebleeds, petechiae on the skin and mucous membranes), hemodynamic instability, severe obstructive disorders (stenosing laryngotracheitis, bronchial obstruction syndrome), acute respiratory failure, primary and secondary pneumonia. Risk factors for severe influenza/ARVI and development of complications are chronic diseases of the cardiovascular system, respiratory system, diabetes mellitus, immunodeficiency conditions, and cancers.

5. Cases not specified by the protocol when, according to the investigator's opinion, further participation in the study harms the patient.
6. Incorrect inclusion of ineligible patient.

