### **Secondary endpoints**

1. Time to normalization of body temperature.
2. Time to alleviation of flu-like nonspecific symptoms.
3. Time to alleviation of respiratory symptoms.
4. Flu-like nonspecific and respiratory symptoms total score (TS) for days 2-6 (according to the patient's diary).
5. ARVI severity (based on the area under the curve of TS for days 2-6, according to the patient's diary).
6. Percentage of patients recovered on day 2, 3, 4, 5, and 6 (according to the patient's diary).

---

 Criteria of alleviation of all ARVI symptoms: body temperature  $\leq 37.5^{\circ}\text{C}$  for 24 hours (without subsequent increase within the observation period) + absence of ARVI symptoms /presence of ARVI symptoms with  $\leq 3$ -point of TS.

 Oral temperature  $\leq 37.5^{\circ}\text{C}$  for 24 hours (without subsequent increase within the observation period).

 Absence of flu-like nonspecific symptoms/presence of one mild flu-like nonspecific symptom.

 Absence of respiratory symptoms/presence of one mild respiratory symptom.

7. Rates of antipyretic use per patient during days 1 to 5 of therapy (according to the patient's diary).
8. Percentage of patients with worsening of illness (ARVI complications, including those requiring antibiotics; hospitalization) for 14 days.

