## Statistical Analyses

### *Samples*

*Total set:* all patients included in the study whose parents/adoptive parents signed the Informed Consent Form for the patient's participation in the study. All AEs will be considered throughout the study for this sample.

*Safety population:* all patients who received at least one dose of the test drug. This sample will be used to **analyze the study therapy safety**, since all the AEs detected in the patient after administration of the drug product will be recorded. The AEs registered in patients of the *Total set* sample from the moment of signing the Informed Consent Form, but before the test drug administration will not be taken into account when analyzing the study therapy safety.

*Full Analysis Set.* This sample includes all the enrolled patients, except for those who have experienced at least one of the following events:

- 1) non-compliance with inclusion / exclusion criteria ;
- 2) the patient has not taken a single dose of the study drug;
- 3) lack of any data of the patient following randomization.

This sample, the most consistent with the "Intention-to-treat" principle, will be used for the **Intention-to-treat analysis (ITT analysis) of the the study therapy efficacy**.

To fill in the missing data (indicators/options), the method "LOCF" (Last Observation Carried Forward)" will be applied.

*Per protocol set.* This sample includes all the patients who have received the complex therapy under the Protocol, completed all the scheduled visits and had no significant deviations from the Protocol. This sample will be used for the **Per Protocol analysis (PP- analysis) of the the study therapy efficacy**.

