### **Evaluation of sample size**

The sample size has been assessed on the basis of the following rules and assumptions:

1. Statistical provisions.
  - 1.1 the power of the statistical tests " $P = (1 - \beta)$ " is assumed to be 80% (the probability of correct rejection of the null hypothesis is 0.8);
  - 1.2 the probability of a type I error " $\alpha$ " is allowed to be less than 5% (the probability of the erroneous acceptance of an alternative hypothesis is less than 0.05);
  - 1.3 the statistical criteria used are 2-sided;
  - 1.4 the calculation of the sample size is based on the assumptions about the expected effects, mainly declared in the primary efficacy criterion of the Protocol;
  - 1.5 statistical null and alternative hypotheses are formulated as follows:

$$H_0: m_2 - m_1 \leq 0$$

$$H_1: m_2 - m_1 > 0,$$

where  $m_1$  – time to resolution of all the disease symptoms in the Ergoferon group,  $m_2$  – time to resolution of all the disease symptoms in the Placebo group;

- 1.6 the sample size of the first and second groups for the two-sided criterion is calculated with the formula:

$$N_1 = N_2 = \sigma^2 (z_\alpha + z_\beta)^2 / (m_2 - m_1)^2,$$

where  $N_1$  and  $N_2$  – sample sizes of the Ergoferon and Placebo groups;  $\sigma$  – expected standard deviation of the first and second groups;  $z_\alpha$  and  $z_\beta$  – z-criterion values for  $\alpha$  and  $\beta$ ;  $m_1$  – time to resolution of all the disease symptoms in the Ergoferon group;  $m_2$  – time to resolution of all the disease symptoms in the Placebo group;

- 1.7 the final sample size is calculated with the following formula:

$$N_F = N_{PP} / (1 - K_B),$$

where  $N_F$  – final sample size;  $N_{PP}$  – result of calculations in par. 1.6, i.e. the planned number of patients completing the study in accordance with the Protocol;  $K_B$  – exclusion rate.

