## 2. Assumptions about the expected effects of the clinical study.

It is assumed that the difference between the average duration of the disease (before recovery / resolution of the disease) in the Ergoferon group and in the Placebo group will be at least 0.5 days, and the standard deviation in both groups will not exceed 1.3 days.

Based on the above statistical rules and assumptions, the size of each group will account for 108 people (sample for the PP analysis).

Given the possible exclusion of the patients during the screening process, as well as in the study for various reasons, it was decided to increase the sample by 25% ( $K_B=25\%$ ) and include at least 288 patients (144 patients in each group).

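### Data after outcome-related withdrawal are not assured, and blanket LOCF can then under-count 14-day worsening and gives the primary endpoint no valid event time

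*Combined protocol and SAP*

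**What the plan says.** Criteria for Withdrawal or Termination is a single list of six reasons. Some concern the drug (an adverse event that requires its cancellation) and some concern the study, such as "Desire of patient or parent/adoptive patient to complete the study ahead of schedule due to inefficacy of therapy or any other reason". Need for a prohibited medicine is also on the list. Prohibited concomitant therapy covers steroids, antivirals and antihistamines, among others, but not antibiotics.

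The primary endpoint is the time from enrolment to alleviation of all symptoms, taken from the diary. Secondary endpoint 8 is "Percentage of patients with worsening of illness (ARVI complications, including those requiring antibiotics; hospitalization) for 14 days". The Study design section schedules a telephone visit on Day 14 ± 1 that asks about complications and antibiotics. It does not say whether withdrawn children are called, or whether their diaries continue.

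Under Samples, the Full Analysis Set leaves out only children who were ineligible, were never dosed, or have no data after randomisation. The missing-data rule follows: "To fill in the missing data (indicators/options), the method" named is last observation carried forward. No endpoint has its own rule. The Per Protocol set requires completion of every scheduled visit.

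**The concern.** Withdrawal for inefficacy or for a prohibited drug depends on how the child is doing, so any data lost afterwards are not lost at random.

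The carry-forward rule then does two different things. On a cumulative yes/no endpoint, a child who leaves before any complication is carried forward as having none, so an unknown outcome becomes a favourable one. On a time-to-event endpoint, carrying a state forward does not produce a time. The analyst would have to choose a day or a censoring rule that the plan does not state. The Per Protocol analysis, on which the sample size rests, removes these children altogether.

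At stake are a count of clinically important events that may be too low, and a primary comparison that depends on an unstated choice.

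**Working it through.** **1. The plan's own figures.** Inputs from Evaluation of sample size and the assumptions that follow it: type I error 5%; "the statistical criteria used are 2-sided"; power 80%; and a difference that "will be at least 0.5 days, and the standard deviation in both groups will not exceed 1.3 days".

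- Two-sample normal formula: n = 2 × 1.3² × (1.960 + 0.842)² / 0.5² = 106.1, so 107 per group. The exact t-test calculation gives 108 (power 80.3%), which matches the plan.
- Inflation: 108 / 0.75 = 144, matching "144 patients in each group", or 288 in all.
- The formula as printed has no factor 2 and would give 54 per group. That is a separate matter and does not affect this point.
- The allowance is 144 − 108 = 36 per group, or 72 of 288. It covers exclusions at screening and during the study together, so 25% is a ceiling for in-study loss and not an estimate of it.
- If all 144 per group were analysed, power for the planned effect would be about 90%.

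**2. What is known after withdrawal.** The withdrawal list does not separate the two kinds of stopping. The schedule does not mention withdrawn children. The Full Analysis Set keeps them, LOCF fills what is missing, and the Per Protocol set drops them.

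**3. Worsening over 14 days (illustration; all rates assumed).** Let w be the share withdrawn before any event, r their true later event rate, and q = 3% the rate in children who stay. Assume no contact after withdrawal.

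- True rate = (1 − w)q + wr
- Rate under LOCF = (1 − w)q
- Events missed per arm of 144 = 144wr

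| w | r | True rate | LOCF rate | Missed per arm | Share of true events |
|---|---|---|---|---|---|
| 5% | 15% | 3.60% | 2.85% | 1.1 | 21% |
| 5% | 30% | 4.35% | 2.85% | 2.2 | 34% |
| 10% | 15% | 4.20% | 2.70% | 2.2 | 36% |
| 10% | 30% | 5.70% | 2.70% | 4.3 | 53% |
| 25% | 15% | 6.00% | 2.25% | 5.4 | 62% |
| 25% | 30% | 9.75% | 2.25% | 10.8 | 77% |

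If withdrawn children carry no extra risk (r = 3%), the loss is 0.2 to 1.1 events per arm (5% to 25%). If they are in fact followed to Day 14, it is zero.

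**4. Primary endpoint (illustration; all rates assumed).** Suppose an unresolved withdrawn child is given the withdrawal day as the event time and truly recovers g days later. With withdrawal shares p1 (Ergoferon) and p2 (placebo), the bias in placebo minus Ergoferon is −(p2 − p1) × g.

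| p1 | p2 | g = 2 d | g = 3 d | g = 5 d |
|---|---|---|---|---|
| 5% | 5% | 0 | 0 | 0 |
| 5% | 10% | −0.10 d | −0.15 d | −0.25 d |
| 10% | 5% | +0.10 d | +0.15 d | +0.25 d |

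In the second row the planned 0.5 d appears as 0.40, 0.35 or 0.25 d. With 144 per group and SD 1.3 d, power falls from 90% to 74%, 63% or 37%. In the third row the effect is inflated by the same amounts. If the analyst instead assigns a day later than true recovery, g is negative and the signs reverse.

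**The case against.** Much of the case on the other side stands.

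- **Silence is not a stop rule.** A reader might infer that a withdrawn child has no later diary and no Day 14 call. The documents do not say so, and the telephone visit is not limited to completers. The text is also headed as a protocol summary, so some procedural silence is to be expected. What can be said is that the data are not assured.
- **These children are not lost from the main analysis.** A reader might infer that the primary endpoint misses the longest illnesses. Withdrawn children who are eligible, dosed and have some data after randomisation stay in the Full Analysis Set, and an unresolved state carried forward keeps them as not recovered. The defect is the undefined time. Survival analysis is listed under Non-parametric criteria but is not tied to the primary endpoint, so it does not fill the gap.
- **The named complications do not themselves cause withdrawal.** Antibiotics are not prohibited and hospitalisation is not a withdrawal criterion. Events recorded by the time of withdrawal count, and children with persisting symptoms or complications have an extra Day 10 visit. Only events after withdrawal are exposed.
- **Direction is not fixed.** More withdrawals on placebo, with times cut short, would shrink the effect and so be conservative. The opposite imbalance would inflate it.

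None of this supplies a rule for the child who leaves unresolved or before an event. LOCF is stated as the method, so this is more than a missing detail.

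**Conclusion.** The point holds in limited form and should be corrected. LOCF is the wrong rule for both endpoints when withdrawal is outcome-related and later data are not assured.

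For endpoint 8, the error per child is one-way: an event after withdrawal can be missed but not invented. Under the assumed rates with excess risk, 1.1 to 10.8 events per arm would be missed. For the primary endpoint, the bias runs from 0 to about ±0.25 d, which is half the planned 0.5 d at the extreme. That extreme needs a 5-point imbalance in withdrawal and a 5-day gap, neither of which comes from the documents.

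The actual size is unknown, because the plan gives no in-study withdrawal rate and no worsening rate. Reading the 25% allowance as expected in-study dropout would overstate the scale, since it includes screening exclusions. Nor do the documents support a claim that the plan favours Ergoferon.

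**What to change.** **Data collection.** State that stopping study drug is not withdrawal from follow-up. Seek diary data and the already scheduled Day 14 call for every randomised child unless the parent refuses contact. Record separately the reason for stopping drug and the reason for leaving follow-up.

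**Primary endpoint.** Do not apply LOCF. Name a survival method as the analysis.

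- Keep children withdrawn unresolved for inefficacy or a prohibited drug, with no later data, as not recovered, censored at the end of the observation period. Name that day: diaries come back at Visit 3 or 4, while observation runs to Day 14.
- Censor other children without further data at the last diary entry.
- Swap the handling in a sensitivity analysis. Censoring everyone at the last entry assumes uninformative dropout, so it should not be the main rule for the outcome-related withdrawals.

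**Endpoint 8.** Do not apply LOCF. Count events up to Day 14 whenever they occur, including after study drug stops. Add a sensitivity analysis that counts unknown Day 14 status as worsened.

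**Reporting.** Show withdrawals by arm and reason, and the number in each arm with unknown Day 14 status.

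**Cost.** Protocol and SAP wording, some extra calls to families of withdrawn children, and modest analysis work. No extra children are needed: 108 per group and 288 in total stand.

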### **Number of subjects**

It is planned to include 288 patients, which is expected to allow completion of all protocol procedures by at least 216 patients (108 patients in the Ergoferon and Placebo groups, exclusion rate is 25%).

### **Interim analysis**

An interim statistical analysis is not scheduled within the study.

### **Treatment**

#### ***Group 1***

**Name of the medicinal product:** Ergoferon

**Active ingredient:** affinity purified antibodies to human gamma interferon – 0.006 g\*, affinity purified antibodies to histamine – 0.006 g\*, affinity purified antibodies to CD4 – 0.006 g\*

*\* Mixture of water-ethanol dilutions 100^12, 100^30, 100^50 of active substance used for saturation of lactose monohydrate.*

**Excipients:** Lactose monohydrate – 0.267 g, microcrystalline cellulose – 0.03 g, magnesium stearate – 0.003 g.

**Method of administration:** Tablet for oral use, 1 tablet per intake (outside a meal/feeding). On day 1, five tablets are taken in the first 2 hours (one tablet every 30 min), followed by three more tablets regularly spaced during the rest of the day (total 8 tablets). From day 2, one tablet is taken every 8 hours. The drug is administered outside a meal (in the interval between meals or 15 minutes before meal or fluid intake). Keep the tablet in the mouth, without swallowing, until completely dissolved. For young children (aged 6 months to 3 years old), the tablet is recommended to be dissolved in a small amount (1 tablespoon) of drinking water of room temperature.

The therapy lasts for 5 days.

**Dosage form:** Tablets.

**Description:** White to off-white, round, flat, scored on one side and beveled tablets.

**Storage conditions:** Store in a dry place protected from light, at the temperature not exceeding 25°C. Keep out of the reach of children.

## ***Group 2***

**Name of the medicinal product:** Placebo

**Active ingredient:** NA

**Excipients:** Lactose monohydrate – 0.267 g, microcrystalline cellulose – 0.03 g, magnesium stearate – 0.003 g.

**Method of administration:** Placebo using Ergoferon scheme.

**Dosage form:** Tablets.

**Description:** White to off-white, round, flat, scored on one side and beveled tablets.

**Storage conditions:** Store in a dry place protected from light, at the temperature not exceeding 25°C. Keep out of the reach of children.

### ***Treatment duration***

Ergoferon/Placebo treatment duration is 5 days.

### ***Observation period***

In total, the patient is observed up for 14 days (screening and randomization up to 1 day, therapy for 5 days, follow-up from 6 to 10 day; delayed telephone “visit” on day 14).

### ***Symptomatic (Standard) treatment***

Throughout the study, patients can receive symptomatic flu/ARVI therapy based on the approved standards of care.

Indications for prescription of antipyretics:

- body temperature over 38.5°C;
- body temperature  $\geq 38.0^\circ\text{C}$  in case of concomitant chronic diseases of the lungs, heart, nervous system.

If an antipyretic was received by the child from parent/adoptive parent independently (without any recommendation by the doctor) and in the absence of indications for use, the patient will not be excluded from the study. The patient’s parent/adoptive parent is recommended to record the thermometry values prior to drug intake, its name and dose in the patient’s diary.

***Drug products allowed for use as antipyretics*** (the ATC group is indicated in brackets):

1. Paracetamol (N02BE01).
2. Ibuprofen (M01AE01).
3. Metamizole sodium (N02BB02) only under prescription (for emergency care at hyperthermia resistant to paracetamol/ibuprofen, parenteral).

The antipyretic drugs (Panadol for children, 120 mg/5 mL or Nurofen® for children, 100 mg/5 mL, suspension for oral administration) will be provided by the Sponsor for all the participants of the study. The doctor prescribes antipyretics which issues to the patient’s

parent/adoptive parent at Visit 1. In accordance with the Instruction for Medical Use, the drug products are allowed for administration in children aged at least 3 months.

***Prohibited concomitant therapy***

Two weeks before inclusion in the study, as well as during the study (from signing of the information sheet for parents/adopters /informed consent form) it is prohibited to administer the following drug products (their ATC group is indicated in brackets):

1. Antivirals (J05), except for Ergoferon prescribed within this study.
2. Immunostimulants (L03), including:
  - interferon inducers (acridonoacetic acid, meglumine acridone acetate/cycloferon®, umifenovir/arbidol®, kagocel®, tiloron/amixin®, polyadenyl acid + polyuridylic acid/poludan®, sodium oxodihydroacridinyl acetate/neovir®, lavomax®, tilaxin®, etc.)
  - interferons;
  - bacterial immunomodulators (including ribomunyl®, sodium ribonucleate/ridostin, etc., sodium deoxyribonucleate/derinat®, etc., IRS-19, imudon®, broncho-munal®, etc.).
  - pidotimod/immunorix;
  - interleukins;
  - synthetic immunostimulants (levamisole, alpha-glutamyl-tryptophan/thymogen, etc.);
  - drug products with thymus hormones;
3. Antihistamines (R06).
4. Fenspiride (R03DX03), omalizumab (R03DX05).
5. Steroidal and non-steroidal anti-inflammatory drugs (except for ibuprofen).
6. Analgesics and antipyretics (except for paracetamol, metamizole sodium).
7. Analgesics/antipyretics combinations for symptomatic therapy of acute respiratory infections.
8. Drug products based on ultra-low doses of antibodies (anaferon (L03AX), epigam, etc).
9. Homeopathic drug products.
10. Immunosuppressants (L04).
11. Antineoplastic agents (L01) and combined (with hormones) antineoplastic endocrine therapy (L02).
12. Immune sera and immunoglobulins (J06).
13. Vaccines (J07).

[figure not shown]
---

 If the patient has taken any drug product listed in “Prohibited Concomitant Therapy” (except for the drugs specified in par. 10-14) once prior to the study, it is not considered an exclusion criterion.

14. Drugs that previously caused hypersensitivity/ allergic reactions in patient.

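### Footnote 8 lets a child who has taken Ergoferon, or another ultra-low-dose antibody product, once before the study be randomised to placebo, which slightly dilutes the comparison

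*Combined protocol and SAP*

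**What the plan says.** The section on prohibited concomitant therapy lists 14 groups of products that may not be used in the two weeks before inclusion or during the study. Two matter here:

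- Item 1: "Antivirals (J05), except for Ergoferon prescribed within this study". Only trial-supplied Ergoferon is carved out, so Ergoferon from any other source falls under the prohibition.
- Item 8: "Drug products based on ultra-low doses of antibodies (anaferon (L03AX), epigam, etc". The Group 1 treatment description gives the test product's active ingredients as dilutions of antibodies, the first being "affinity purified antibodies to human gamma interferon", so it belongs to the same kind of product.

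Footnote 8 then relaxes the pre-study part of the rule for one intake of a listed product: "except for the drugs specified in par. 10-14) once prior to the study, it is not considered an exclusion criterion". The exemption therefore reaches items 1 to 9, including items 1 and 8.

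Exclusion criterion 8 is consistent with the footnote. It begins "Course administration of the drug products specified in the section" and applies to the two weeks before inclusion, so it bars a course but not an isolated dose. Children enter under inclusion criterion 3: "First 24 hours after ARVI onset".

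The Full Analysis Set (FAS) drops children for "non-compliance with inclusion / exclusion criteria", for taking no study drug, or for having no data after randomisation. The Per Protocol (PP) set drops those with incomplete therapy or visits, or with significant protocol deviations.

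**The concern.** In a placebo-controlled trial, a control child should not have had the test product for the illness under study. Footnote 8 is written by item number. A tolerance that is easy to understand for, say, one antihistamine dose therefore extends to the test product and its class. The footnote sets no minimum interval and does not place the intake before the current illness. With entry in the first day of illness, a dose at home that morning followed by randomisation to placebo complies fully with the plan.

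Nothing downstream deals with such a child. The child meets the criteria and has not deviated, so stays in both the FAS and the PP set. Concomitant therapy is recorded at Visit 1, but the statistical section plans no stratification, covariate or sensitivity analysis on prior exposure. If the product works as the plan assumes, any effect of that dose in a placebo child narrows the observed difference and costs power.

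**Working it through.** **1. Does the exemption reach the test product?**

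| Provision | Effect on one earlier intake of Ergoferon or a sister product |
|---|---|
| List item 1 | Off-study Ergoferon is a prohibited product |
| List item 8 | Ultra-low-dose antibody products are prohibited |
| Footnote 8 | One intake forgiven unless in items 10-14; items 1 and 8 are not |
| Exclusion criterion 8 | Bars a course only |
| Other exclusion criteria | None addresses it |
| FAS and PP definitions | Child retained in both |

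The answer is yes. It rests on inference for Ergoferon, which is not named as a barred earlier drug: its coverage follows from the wording of item 1 and the open-ended class in item 8.

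**2. Reproducing the plan's sample size.** Inputs from the sample size section: difference 0.5 day, SD 1.3 days, two-sided α = 0.05 ("the probability of the erroneous acceptance of an alternative hypothesis is less than 0.05"), power 0.80.

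- Normal approximation: n = 2σ²(z₀.₉₇₅ + z₀.₈₀)²/Δ² = 2 × 1.69 × 7.849 / 0.25 = 106.1, so 107 per group.
- t-test solution: 107.09, so 108 per group. This matches the stated 108.
- Inflation: 108 / (1 − 0.25) = 144 per group, 288 in total. This matches.

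(The formula as printed lacks the factor 2 and would give 53.06, so 54 per group. The stated 108 is the standard two-sample result, so 108 is used here.)

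**3. Dilution model.** Let f be the share of placebo children with one earlier intake and c the fraction of the full treatment effect that intake carries. The documents give neither, so both are assumptions. Assuming no added benefit in the active arm:

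Δ(f, c) = 0.5 × (1 − f × c)

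For a carry-over proportional to tablets, the regimen gives 8 tablets on Day 1 and one every 8 hours from Day 2. That is 8 + 4 × 3 = 20 over 5 days. One tablet is 1/20 of the course or 1/8 of Day 1.

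**4. Power**, two-sided t-test, SD 1.3, 108 per group:

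| f | c | Difference (days) | Power |
|---|---|---|---|
| 0 | – | 0.500 | 0.803 |
| 10% | 1/20 | 0.4975 | 0.799 |
| 10% | 1/8 | 0.494 | 0.793 |
| 5% | 1/2 | 0.4875 | 0.783 |
| 10% | 1/2 | 0.475 | 0.762 |
| 5% | 1 | 0.475 | 0.762 |
| 10% | 1 | 0.450 | 0.716 |

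With proportional carry-over the loss at f = 10% is 0.4 to 1.0 percentage point. In the last row, where one intake does the work of the whole course, it is 8.7 points.

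**5. Larger analysis set.** The FAS could hold up to 144 per group. There, even f = 10% with c = 1 leaves power at 0.833; at 126 per group it is 0.781.

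**The case against.** The strongest reply is that this is a deliberate rule, applied consistently. Footnote 8 and exclusion criterion 8 both separate isolated use from a course, and items 10 to 14 are knowingly held stricter. Every entrant must still have a temperature of at least 38.0°C and a symptom score of at least 5 at examination. The primary endpoint runs from enrolment. The Visit 1 schedule already includes medical history, concomitant therapy and the eligibility check. All of this stands. The documents do not contradict themselves here; the question is whether the trade-off should extend to the test product.

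Four stronger readings are tempting, and the documents do not support them:

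- *Any earlier user of Ergoferon can enter.* Only a single intake is exempt; a course within two weeks excludes.
- *The loading phase may already have been given.* Five of the eight Day 1 tablets fall in the first 2 hours, so a reader might infer that a child could arrive already loaded. The regimen, however, counts one tablet as one intake, so those are five intakes. The footnote does not define a single use, but on the protocol's own usage it is one tablet.
- *Power falls to about 0.72.* That needs an assumed 10% exposure and full carry-over from one intake. The documents say nothing about use at home. Exposure also occurs in the active arm, where any benefit would offset part of the dilution.
- *The gap favours Ergoferon.* Exposure precedes blinded randomisation and is expected to balance between arms. The expected direction is toward no difference.

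**Conclusion.** The gap is real and the text settles it: one earlier intake of off-study Ergoferon or of an item 8 product, possibly in the same illness, does not prevent randomisation or inclusion in either efficacy set. Its likely consequence is a small dilution toward zero. At an assumed 10% of placebo children exposed, with carry-over proportional to tablets, power at 108 per group is about 0.79-0.80 against 0.80 as planned. The figure of 0.72 is an extreme upper bound on the harm, not an expectation. These sizes depend on two quantities that the documents do not give, the exposure rate and the carry-over, and on reading a single use as one tablet. The point neither invalidates the design nor changes the stated sample size. It is worth making because the correction is cheap and leaves the placebo arm free of the test product at entry.

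**What to change.** In footnote 8, except Ergoferon taken outside the study and all item 8 products from the single-intake exemption. In exclusion criterion 8, add that any intake of these within the existing two-week window excludes, so that the two provisions agree. Ask about them by name in the Visit 1 history, before randomisation. Where the exemption remains for other products, state what counts as a single use.

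The cost is a few more screen failures, at a visit where medication history is already taken. The sample size and the planned analyses stay as they are.
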